6. MEASUREMENT OF TREATMENT COMPLIANCE

Compliance with study drug will be monitored closely and determined at each visit. Subjects and their parent(s)/legal guardian(s) will be instructed to bring all unused study drug with them to the Day 15 visit. Compliance will be assessed by counting capsules and dividing the actual number of doses taken (per capsule count) by the number of doses the subject should have taken within a visit period and multiplying by 100. Subjects who miss more than 25% of scheduled doses or take more than 125% of the scheduled doses will be considered noncompliant. Treatment compliance (number of missed days) and treatment exposure (e.g. time in trial, time on treatment) will be tabulated overall and by the following groups: <75%, 75%-125%, and >125%. Subjects who are lost to follow-up and/or subjects who do not return unused study drug will have missing compliance data.

Each subject's compliance and treatment exposure data will be listed.

7. EFFICACY EVALUATION

7.1 Overview of Efficacy Analysis Issues

7.1.1 Handling of Dropouts or Missing Data

Missing data could occur under either or both of the following scenarios: (1) missing or invalid data for individual questions in the SKAMP; and (2) missing SKAMP-CS at individual time points. The approach to handling missing data under these scenarios is described below.

7.1.1.1 Missing Individual Items in the SKAMP Scale

The SKAMP scale is a 13-item independent observer rating of subject impairment of classroom observed behaviors. Each item is rated on a 7-point impairment scale (0 = normal to 6 = maximal impairment). The combined scores for the SKAMP are obtained by summing the values of corresponding items in the assessment.

Missing or invalid data for individual questions will be handled by rules specific to the validated SKAMP scale as follows:

- If 3 or more individual items in the SKAMP have missing or invalid data, the SKAMP-CS will be set to missing.
- If 1 or 2 individual items in the SKAMP are missing or invalid, the values for the missing individual items will be imputed using the mean of the non-missing individual items for the particular subject at that visit, rounded to the nearest integer.
- If any item within a SKAMP subscale is missing or invalid, the entire subscale score will be set to missing.

7.1.1.2 Missing SKAMP Combined Scores at Individual Time Points

Primary Analysis

No imputation of missing SKAMP-CS at individual time points will be done for the primary efficacy analysis. Subjects with missing SKAMP-CS data at all individual time points at either the baseline or Day 15 visit will not be included in the primary analysis.

Sensitivity Analyses

To explore the robustness of the primary efficacy analysis of the change from baseline at Day 15 in ADHD symptoms in mean SKAMP-CS, 3 sensitivity analyses of the

primary analysis may be performed: a placebo-based multiple imputation (MI) pattern-mixture model (PMM) analysis and a tipping point analysis using the PMM.

Sensitivity analysis one: Placebo-based MI PMM

To explore the robustness of the primary analysis results, a sensitivity analysis will be carried out that assesses the situation where the data are not missing at random (NMAR). More specifically, all subjects taking dasotraline who discontinue for any reason will be assumed to behave like placebo subjects.

A controlled, multiple imputation approach based on PMM will be applied for those subjects on dasotraline using the 'Copy Reference' approach [4]. More specifically, missing data for those subjects taking dasotraline who discontinued will be imputed based on the posterior distribution of the placebo group. Missing data for placebo subjects who discontinued will also be imputed using the observed values of the placebo group.

Data will be imputed using SAS PROC MI (v9.3 or later) using the full conditional specification method (FCS). Twenty burn-in iterations will be performed prior to each imputation. The imputation model will include clinical site, observed non-missing baseline SKAMP-CS, observed non-missing baseline PERMP scores, age, and sex. One hundred imputed datasets will be generated for analysis.

The same model used in the primary analyses will be fit to each of the 100 datasets. The parameter estimates and standard errors will be combined using PROC MIANALYZE in SAS v 9.3 or higher.

Sensitivity analysis two: Tipping Point Analysis using PMM

The goal of the tipping point analysis is to determine how robust the results of the primary analysis are to varying its assumption that the change from baseline at Day 15 mean SKAMP-CS for subjects that discontinue from the dasotraline group is the same as the completers in the dasotraline group. In particular, this analysis examines how altering this assumption to allow the discontinued subjects to have better and worse outcomes will impact the resulting estimates of the treatment effect. This will quantify the range of values which the assumptions can take on and still provide the same conclusions as the primary analysis, giving a very direct measure of the sensitivity of the primary analysis to deviations from the assumptions using an approach that has missing values for dasotraline discontinuation subjects imputed. Data will be imputed using the same imputation model and methods described in the first sensitivity analysis.

In this analysis, the estimate of the effect in the dasotraline subjects may be viewed as a weighted average of the observed average for dasotraline completers and the

average MAR estimate for dasotroline subjects. This can be approximated as:

$(1-p) * [\text{Avg (dasotroline completers)}] + (p * \Delta * [\text{MAR estimate for dasotroline subjects}]),$

where p is the proportion of subjects in the dasotroline group that discontinue early and Δ is the shift parameter. By varying Δ , the potential impact of the imputations for subjects with missing data on the final estimate will be assessed. Shift values of .05 (treated subjects have 5% of the change from baseline SKAMP-CS as assumed in the primary methodology) through 1 (treated subjects have 100% of the change from baseline SKAMP-CS as assumed via the primary methodology) will be applied at increments of .05 and reported. The primary analysis will be rerun for all values of Δ and the resulting treatment difference, 95% CI and p-value for each Δ will be reported; the wider the range of values that result in no change in interpretation, the more robust the analysis results may be considered to be.

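### The tipping-point grid for the primary endpoint does not cover the better and worse outcomes it promises, and the width of its non-tipping range is not a direct measure of robustness

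*SAP*

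**What the plan says.** The primary ANCOVA imputes no missing time points and leaves out children with no SKAMP-CS at all at baseline or at Day 15 (SAP 7.1.1.2). Protocol 15.3.8 names two checks on it, a placebo-based pattern-mixture model and a tipping-point analysis, and leaves the detail to the SAP.

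For the tipping-point analysis, SAP 7.1.1.2 says:

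- Aim: "altering this assumption to allow the discontinued subjects to have better and worse outcomes".
- Formula: the dasotraline mean is (1 - p) times the completers' average plus p times Delta times the "average MAR estimate for dasotroline subjects", where p is the proportion who discontinue (written q below, to keep it apart from p-values).
- Grid: "Shift values of .05 (treated subjects have 5% of the change from baseline SKAMP-CS as assumed in the primary methodology) through 1", in steps of 0.05. Delta = 1 means that "treated subjects have 100% of the change from baseline SKAMP-CS as assumed via the primary methodology".
- Claim: the analysis is described as "giving a very direct measure of the sensitivity of the primary analysis to deviations from the assumptions".
- Reading rule: "the wider the range of values that result in no change in interpretation, the more robust the analysis results may be considered to be".
- Imputation: "Data will be imputed using the same imputation model and methods described in the first sensitivity analysis". In that first analysis, "missing data for those subjects taking dasotraline who discontinued will be imputed based on the posterior distribution of the placebo group".

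The treatment difference, 95% confidence interval and p-value are reported for every Delta.

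**The concern.** There are three problems.

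1. **The grid does not match the aim.** Lower SKAMP-CS is better. If dasotraline children improve on average, Delta = 1 is the best mean tested and equals the primary assumption, while Delta = 0.05 still leaves a slight mean improvement. No better mean is tried, and none at or beyond zero change. This concerns arm means; individual imputed values can be worse than baseline. If the arm's mean change is near zero the grid barely moves the estimate, and if it is a worsening, lowering Delta favours the drug.
2. **The reading rule depends on something other than robustness.** A multiplier on change from baseline has a reach set by the size of that change, part of which is common to both arms. Two trials with the same treatment difference and the same missing data can then get different verdicts.
3. **The starting imputation is not pinned down.** Most of the text points to MAR in the dasotraline arm, but the sentence on imputation can be read as Copy Reference.

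What is at stake is the credibility of one of the two planned checks in the situations where it would be needed: a borderline result, or more dropout than planned.

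**Working it through.** **Inputs.** Difference 4.0, SD 5, 50 completers per arm, two-sided 5% (SAP 2.6). The target of 110 randomised for 100 completers implies about 5 of 55 missing per arm, so q = 5/55 = 0.091. The documents give no expected placebo change; +2, 0, -2 and -4 points are assumptions. So is the borderline difference of 2.25.

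**The plan's own figure.** SE = 5 x sqrt(2/50) = 1.0. The t-test power for 4.0 points is 97.7%, consistent with the stated floor of 95%. The critical value (98 df) is 1.984, so a difference below about 1.98 points is not significant.

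**Arm-mean calculation, using the SAP's formula.** Let m be the placebo change, d the size of the difference, and c = m - d the dasotraline change. The SE is held at 1.0.

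- Estimate at Delta: (1 - q)c + q x Delta x c - m
- Largest penalty per dropout: 0.95 x |c|
- Delta at which the result tips: 1 - (d - 1.984)/(q x |c|)
- Additive shift at which it tips: (d - 1.984)/q, which does not involve m

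*Design case, d = 4.0.* At m = 0 the estimate moves from -4.00 to -4 x (1 - 0.95 x 0.091) = -3.65. Over m = +2 to -4 the value at Delta = 0.05 runs from -3.83 to -3.31, with p at most 0.0013. The additive tip is (4 - 1.984)/0.091, about 22 points.

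*Borderline case, d = 2.25 (p = 0.027 at Delta = 1).*

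| Placebo change m | +2 | 0 | -2 | -4 |
|---|---|---|---|---|
| Dasotraline change c | -0.25 | -2.25 | -4.25 | -6.25 |
| Largest penalty (points) | 0.24 | 2.14 | 4.04 | 5.94 |
| p at Delta = 0.05 | 0.028 | 0.0425 | 0.063 | 0.090 |
| Delta at tip | -10.7 | -0.30 | 0.31 | 0.53 |
| Additive tip (points) | 2.9 | 2.9 | 2.9 | 2.9 |

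The first two tips lie below the grid's floor, so the analysis would report that nothing tips; in the last two it would report a tip. The difference and the missing data are the same in all four.

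**Multiple-imputation check.** 50 completers per arm with exact means and SD 5, 5 missing per arm (45 and 10 in the last row), normal imputation within arm, 20,000 imputations, Rubin's rules, no covariates; each imputed dasotraline change is multiplied by Delta.

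| Placebo change m (d = 2.25) | +2 | 0 | -2 | -4 |
|---|---|---|---|---|
| p at Delta = 0.05, 5/55 missing | 0.022 | 0.035 | 0.055 | 0.086 |
| First tipped grid value, 5/55 | none | none | 0.15 | 0.40 |
| First tipped grid value, 10/55 (p = 0.036 at Delta = 1) | none | 0.20 | 0.70 | 0.80 |

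The additive tip is about 2.8 points in every 5/55 column and 0.8 in every 10/55 column.

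- At m = +2 the nominally harshest setting gives a smaller p (0.022) than Delta = 1 (0.027). Scaling shrinks the imputed spread (SE 1.004 to 0.958) while the mean hardly moves.
- If the dasotraline arm worsens by 2 points (m = +4.25), the estimate goes from -2.25 to -2.42 and p from 0.027 to 0.013 as Delta falls: the check runs in the drug's favour.
- At d = 4.0 the largest p is again about 0.0013. The additive tip is 17.5 points, lower than 22 because a large shift also raises the SE.

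**How often a borderline result would arise.** With SE 1.0, an observed difference of 1.98 to 2.25 has probability 1.8% if the true difference is 4.0 and 9.8% if it is 2.5.

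**Copy Reference reading.** Dropouts at Delta = 1 then take the placebo mean, so the estimate is (1 - 0.091) x (-4.0) = -3.64 rather than -4.00, or -2.05 rather than -2.25. Delta = 1 would repeat sensitivity analysis one and would no longer match the SAP's definition of that value.

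**The case against.** Several points on the other side are sound.

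- The missing better side cannot overturn a favourable significant result, so that omission is a mismatch of wording only.
- Baseline is a washed-out, symptomatic state, so asking what happens if dropouts lose nearly all their improvement is a fair question with a natural end near zero. If placebo improves by 2 or 4 points, Delta = 0.05 is already harsher than placebo-like, and sensitivity analysis one covers placebo-like outcomes separately.
- A multiplier is not an error in itself. Trials in which the drug arm changed by -0.25 and by -6.25 do differ in how much improvement can be lost, and the reader sees the estimate and p-value at every Delta.
- The consequence is confined to a narrow range. With 5/55 missing, a difference of 2.5 tips in only one of the four placebo settings, at the last grid value (p = 0.052), and a difference of 3 never tips (largest p 0.018).
- The exact tipping values are less precise than they look. With the SAP's 100 imputations they ranged over 0.05-0.25 (m = -2) and 0.35-0.50 (m = -4) across 12 seeds, and the check omits the baseline and site terms. The fall in p to 0.022 appears only when individual draws are scaled; the arm-mean formula gives 0.028.
- MAR is the better reading of the imputation text.

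These points limit the size of the problem but do not remove it. The SAP promises exploration in both directions and a direct measure of sensitivity, and its rule equates a wide non-tipping range with robustness. With this grid, a full-width non-tipping range may reflect nothing more than a small change from baseline in the drug arm.

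**Conclusion.** The concern holds. The mismatch between aim and grid, and the dependence of the grid's reach on the change common to both arms, follow from the SAP's text and formula without any outside figure. The size rests on assumed placebo changes of +2 to -4, an assumed borderline difference, SD 5, and 5 or 10 of 55 missing per arm. Under those assumptions the same borderline result is reported as never tipping or as tipping at about 0.40 (5/55) or 0.80 (10/55), while the additive tip stays at about 2.8 and 0.8 points respectively.

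At the planned effect and dropout the result is robust and the grid says so. The primary test, its alpha and its power are not affected. The imputation wording is an ambiguity that one sentence resolves. This should be corrected, but the primary result does not depend on it.

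**What to change.** Amend SAP 7.1.1.2, sensitivity analysis two, before unblinding:

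1. State the starting point: missing Day 15 mean SKAMP-CS is imputed under MAR within randomised arm, with the FCS settings, covariates and 100 datasets of sensitivity analysis one but without its Copy Reference step.
2. Extend the grid in both directions and run it until significance is lost or the scale limit is reached (13 items scored 0 to 6, so 0 to 78). Preferably add shifts of 0, 1, 2, ... SKAMP points to the imputed dasotraline values, with a few negative shifts to honour the stated aim. The 0.05 to 1 multiplier grid can stay alongside as a loss-of-improvement analysis.
3. Replace the rule based on the width of the Delta range: report the tipping shift in points beside the estimated treatment difference, so that readers can judge whether a shift of that size is plausible.

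The cost is SAP wording and a standard delta-adjustment step in the imputation program. No data collection or design element changes.

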7.1.2 Multicenter Studies

This study will have up to 5 different clinical sites enrolling and treating subjects. Each site is expected to have a minimum of 12 subjects. For all efficacy analyses where investigative site is an explanatory effect and in by-site subgroup analyses, pooling of sites should not be necessary and is not planned.

7.1.3 Assessment Time Windows

Data will be summarized based on the recorded visit; no visit windowing will be conducted. Visits 4 (Day 1) and 5 (Day 15) must be performed as scheduled based on the protocol, allowing for consistent and reliable efficacy measurements.

7.2 Efficacy Measurements

7.2.1 Swanson, Kotin, Agler, M-Flynn, and Pelham (SKAMP) Rating Scale

The SKAMP rating scale is a 13-item independent observer rating of subject impairment (7-point scale) of analog classroom-observed behaviors during the laboratory classroom assessments. Items 1-4 represent an indication of subject attention, items 5-8 are an indication of deportment, items 9-11 assess quality of work, and items 12-13 assess subject compliance with teacher and classroom rules. The specific items associated with these subscales are detailed in Appendix 14.3. In this study, the change from baseline at Day 15 in mean total score of all SKAMP items (or SKAMP-CS) is defined as the primary efficacy parameter. The mean SKAMP-CS on Day 15, the SKAMP-CS at each of the post-dose assessment times on Day 15, the change from baseline at Day 15 in SKAMP-CS at each of the post-dose assessment times, the change from baseline

at Day 15 in mean SKAMP-Attention subscale scores (items 1-4), the SKAMP-Attention subscale scores at each of the post-dose assessment times on Day 15, the change from baseline at Day 15 in SKAMP-Attention subscale scores at each of the post-dose assessment times, the change from baseline at Day 15 in mean SKAMP-Depoerty subscale scores (items 5-8), the SKAMP-Depoerty subscale scores at each of the post-dose assessment times on Day 15, and the change from baseline at Day 15 in SKAMP-Depoerty subscale scores at each of the post-dose assessment times are secondary outcome measures. Higher SKAMP-CS scores signify greater behavioral impairment. Therefore, decreases in SKAMP-CS scores over time will indicate improvement in behavior while increases in SKAMP-CS scores over time will indicate worsening of behavior.

The SKAMP rating scale will be collected during each of 7 class sessions at Visits 4 (Day 1) and 5 (Day 15), occurring at 8:00 am, 10:00 am, 12:00 pm, 2:00 pm, 4:00 pm, 6:00 pm, and 8:00 pm of the laboratory classroom days. Three practice classroom sessions for the laboratory classroom day will be conducted at Visit 2.

Missing or invalid data for individual questions will be handled by rules specific to the validated SKAMP scale as described in Section 7.1.1.1.

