11.3. Efficacy Assessments

Swanson, Kotkin, Agler, M-Flynn, and Pelham (SKAMP) Scale

The SKAMP is a validated 13-item rating scale that assesses manifestations of ADHD in a classroom setting through a combined score and 2 subscale scores; deportment items (interacting with other children, interacting with adults, remaining quiet, staying seated, complying with the teacher's directions, and following the classroom rules) and attention items (getting started, sticking with tasks, attending to an activity, making activity transitions, completing assigned tasks, performing work accurately, and being neat and careful while writing or drawing).

Permanent Product Measure of Performance (PERMP)

The PERMP is a 5-page math test consisting of 80 problems per page (total of 400 problems). Both attempted problems and correct problems will be assessed. Subjects are to complete as many problems as possible in 10 minutes.

The appropriate math level for each subject is determined based on results of a math pretest administered at screening.

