12.2 Changes in the Analysis Planned in the Protocol

No changes are planned as of the date of the SAP.

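### The SAP scores SKAMP-Attention and SKAMP-Deportment on 4 items each where the protocol has 7 and 6, and declares no change

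*SAP*

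**What the plan says.** Protocol Section 11.3 describes the SKAMP as a 13-item scale that "assesses manifestations of ADHD in a classroom setting through a combined score and 2 subscale scores". Every item is assigned to one of the two. The first group is "deportment items (interacting with other children, interacting with adults, remaining quiet, staying seated, complying with the teacher's directions, and following the classroom rules", which makes six. The second is "attention items (getting started, sticking with tasks, attending to an activity, making activity transitions, completing assigned tasks, performing work accurately, and being neat" and careful in written work, which makes seven. The synopsis carries the same lists. Protocol Section 6.2 then names SKAMP-Attention and SKAMP-Deportment scores as secondary endpoints, and the protocol offers no other definition of either.

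SAP Section 7.2.1 uses four groups: "Items 1-4 represent an indication of subject attention, items 5-8 are an indication of deportment, items 9-11 assess quality of work", followed by a two-item compliance group. Appendix 14.3 repeats the four groups in a table. Section 7.2.1 also puts the item numbers into the outcomes: the change "at Day 15 in mean SKAMP-Attention subscale scores (items 1-4") for Attention, and "subscale scores (items 5-8") for Deportment. SAP Sections 7.4.2 and 7.5.2 list the secondary outcomes under the protocol's names and include no outcome for quality of work or compliance. On departures from the protocol's analysis, SAP Section 12.2 states: "No changes are planned as of the date of the SAP".

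**The concern.** Which items are summed is part of what an endpoint is. Under the SAP, the Attention result would contain nothing on completing work, accuracy or neatness, and the Deportment result nothing on following directions or rules. A reader holding the protocol would see familiar endpoint names and a statement that nothing had changed, and could not tell that the scores differ in content and range.

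The item set also decides which classroom sessions are analysed, because SAP Section 7.1.1.1 sets a subscale to missing when any one of its items is missing. A smaller issue is that the protocol supports one scoring and the SAP another, with nothing to say which governs.

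**Working it through.** **1. Item mapping** (Protocol Section 11.3 against SAP Appendix 14.3)

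| SAP item | Content | Protocol subscale | SAP subscale |
|---|---|---|---|
| 1-4 | starting, sticking with tasks, attending, transitions | Attention | Attention |
| 5-8 | other children, adults, quiet, seated | Deportment | Deportment |
| 9-11 | completion, accuracy, neatness | Attention | Quality of work |
| 12-13 | directions, rules | Deportment | Compliance |

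Both documents give 13 items in total:
- Protocol: 7 + 6 = 13.
- SAP: 4 + 4 + 3 + 2 = 13.

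The same 13 items are therefore partitioned differently. Three leave Attention and two leave Deportment, so 5/13 = 38% are in neither subscale endpoint.

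**2. Score ranges** (each item scored 0 to 6, SAP Section 7.1.1.1; maximum = items × 6)

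| Score | Protocol | SAP |
|---|---|---|
| Attention | 7 × 6 = 42 | 4 × 6 = 24 |
| Deportment | 6 × 6 = 36 | 4 × 6 = 24 |
| Sum of the two | 78 | 48 |
| Combined score, 13 × 6 | 78 | 78 |

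Under the protocol the two subscales add up to the combined score. Under the SAP they cover 48 of its 78 points.

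**3. Comparisons affected** (SAP Section 7.4.2)

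- Attention: 1 daily-mean change + 7 time-point scores + 7 time-point changes = 15.
- Deportment: 15 by the same count.
- SKAMP-Combined: 1 daily-mean score + 7 + 7 = 15.
- PERMP: 2 measures × (7 + 7) = 28.
- Total: 15 + 15 + 15 + 28 = 73, of which 15 + 15 = 30 rest on the changed subscales.

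**4. Missing subscale scores.** The documents give no item-missing rate. Assume items are missing independently with probability q between 1% and 5%. A subscale of k items is then missing with probability 1 − (1 − q)^k.

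| k | q = 1% | q = 5% |
|---|---|---|
| 4 | 3.9% | 18.5% |
| 6 | 5.9% | 26.5% |
| 7 | 6.8% | 30.2% |

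The two scorings would thus be analysed on different sets of sessions. This illustrates the dependence on item count and is not a forecast.

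**5. What does not move.** The primary endpoint sums all 13 items in both documents. With the planned 50 per arm, a difference of 4.0 and an SD of 5, a two-sided 5% t-test with 98 df has power 0.977. That agrees with the stated figure of at least 95% and does not depend on the subscales.

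**The case against.** The mismatch itself is hard to dispute: it stands in running text and again in an appendix table. The case on the other side concerns its weight.

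- **No confirmatory claim depends on it.** The subscales are secondary, with no hierarchy and no multiplicity adjustment (Protocol Section 15.3.5.4), and the five items remain in the combored total that forms the primary endpoint. This is true and limits the consequence. It does not make the SAP's scores the protocol's scores.
- **The SAP is unambiguous.** It gives one derivation, in two places, and SAP Section 4 requires the SAP to be signed before unblinding, so a programmer following it has nothing to choose. This largely stands, and the risk of choosing a scoring after unblinding is minor. The defect that remains is an undeclared departure from the protocol.
- **The item lists sit in the protocol's description of the scale, not in its endpoint section.** That is so, but they are the only definition the protocol provides for the named endpoints.
- **Thirty comparisons overstates the distinct tests.** In an ANCOVA that adjusts for the same variable's own baseline, the Day 15 score and the change from baseline give the same treatment difference and p-value. If the SAP's model is read that way, there are 8 distinct tests per subscale, or 16. Thirty is a count of listed comparisons.
- **The documents do not show which scoring was intended.** This stands, and the remedy has to allow for either.

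**Conclusion.** The concern holds. Followed exactly, the SAP would report two families of secondary endpoints under the protocol's names on different item sets: 4 items instead of 7 for Attention and 4 instead of 6 for Deportment. Maxima fall from 42 to 24 and from 36 to 24, five of 13 items are in neither subscale, and 30 of 73 listed secondary comparisons are affected. These figures come from counting items and endpoints and need no assumption beyond the stated 0 to 6 item range.

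The effect on treatment estimates or conclusions cannot be quantified, since the documents contain no item-level data. The primary endpoint, the SKAMP-Combined and PERMP endpoints, sample size, power and alpha are untouched. It must still be corrected, because the SAP is wrong as written against its own statement that nothing changed.

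**What to change.** In SAP Section 7.2.1 and Appendix 14.3, define SKAMP-Attention as items 1-4 plus 9-11 (7 items, 0-42) and SKAMP-Deportment as items 5-8 plus 12-13 (6 items, 0-36). This matches the protocol and makes Section 12.2 correct on this point. The 4-item scores may be kept as supplementary analyses.

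If the sponsor intends the 4-item scoring, amend the item lists in the protocol synopsis and Section 11.3, and record the change with its reason in SAP Section 12.2. In either case, settle it before unblinding and state explicitly that the any-item-missing rule in Section 7.1.1.1 applies to the chosen item sets.

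The cost is SAP wording and one derivation change before database lock. All 13 items are already collected for the combined score, so no new data are needed and the sample size does not change.
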